### **3 Study Implementation**

#### **3.1 Study Design**

The primary objective of this study is to determine whether pulmonary metastasectomy and treatment with saracatinib, versus pulmonary metastasectomy and treatment with placebo, results in an increase in progression free survival. A secondary objective is to determine whether pulmonary metastasectomy and treatment with saracatinib, versus pulmonary metastasectomy and treatment with placebo, results in an increase in overall survival. Patients will be eligible for the study following the histological verification of recurrent osteosarcoma. Patients will be stratified based on the number of recurrences (FIRST versus SECOND versus THIRD or MORE) and the number of recurrent nodules (ONE or TWO versus THREE or MORE).

Randomization will occur following complete resection of all lung nodules and the histological verification of recurrent osteosarcoma.

Patients who are randomized to the saracatinib arm will receive saracatinib, 175 mg, orally, once daily, for a 28-day cycle, with no breaks between cycles. The total duration of treatment with saracatinib will be **thirteen 28-day cycles** (364 days total). Patients will receive one 125 mg tablet (9.5 mm diameter) and one 50 mg tablet (7 mm diameter).

Patients who are randomized to the placebo arm will receive placebo, orally, once daily, for a 28-day cycle, with no breaks between cycles. The total duration of treatment with placebo will be **thirteen 28-day cycles** (364 days total). Patients will receive one 9.5 mm tablet and one 7 mm tablet. These tablets will be indistinguishable from saracatinib.

Patients who recur in the lung while on-study and who are thought to be completely resectable will be unblinded. Those patients who were receiving placebo will be offered the opportunity to undergo additional surgical resection, followed by treatment with Saracatinib. If fully resected, they will then begin oral therapy with saracatinib. Saracatinib will be administered as a once daily, oral dose of 175 mg, for a 28-day cycle, with no breaks between cycles. The duration of treatment with saracatinib will be thirteen 28-daycycles (364 days total).

Patients will be followed for the duration that this study is open. If accrual rates proceed as projected, the total duration of this study will be six years.

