#### Toxicity

- Life threatening toxicity as a result of saracatinib/placebo
- Patients who have persistent toxicity despite appropriate dose modifications
- Any unacceptable toxicity in the opinion of the Principal Investigator

Patients who are taken off study will continue to be monitored for survival determination, annually by contacting the referring/treating physician, for the duration that this study is open or a maximum of 3 years follow up.

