## **5.3 Statistical Considerations**

The primary goal of this study is to determine whether the addition of saracatinib to surgery will result in an improvement in progression free survival (PFS). The sample size will be based on being able to detect a 60% relative improvement (from 33% to 53%) in PFS probability at two years. The current 2-year PFS probability is 33%, when a second surgical complete remission is achieved (3). Assuming exponential survival curves, the hazard rate corresponding to this 2-year PFS probability for the control arm is 0.0462, which is defined as approximately a 0.0462 probability of failing each month when the 2-year PFS probability is 33%. If we assume that the 2-year PFS probability may be 53% for the saracatinib arm, the hazard is 0.0265, which then results in a hazard ratio of 1.75. Forty-four patients will need to be randomized in each arm of the study, for a total of 88 patients, over a 48-month accrual period. Follow-up of the last patient randomized must continue for an additional year. Since this study follows a phase II.5 design (35), this provides 80% power to detect a difference between the two resulting actuarial curves with a one-sided 0.10 alpha level log-rank test.

A secondary goal of this study is to determine whether the addition of saracatinib to surgery will result in an improvement in overall survival (OS). The sample size selected to evaluate PFS will also be adequate to detect a 56% relative improvement (from 45% to 70%) in OS probability at three years. The current 3-year OS probability is 45%, when a second surgical complete remission is achieved (3). Assuming exponential survival curves, the hazard rate corresponding to this 3-year OS probability for the control arm is 0.0222, which is defined as approximately a 0.0222 probability of failing each month when the 3-year OS probability is 45%. If we assume that the 3-year OS probability may be 70% for the saracatinib arm, the hazard is 0.0099, which then results in a hazard ratio of 2.24. Evaluation of the 88 patients who are randomized, over the same time frame, will provide 85% power to detect a difference between the two resulting actuarial curves with a one-sided 0.10 alpha level log-rank test.

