### Suggested Follow-up

Study Month	End of Trmt 13 mo	15 mo	18 mo	21 mo	24 mo	30 mo	36 mo
Interim History	X	X (d)	X	X (d)	X	X (d)	X
Physical Examination	X	X (d)	X	X (d)	X	X (d)	X
Weight, Height, Vital Signs	X	X (d)	X	X (d)	X	X (d)	X
Laboratory Tests	X		X		X		X
Thoracic CT	X		X		X		X
Bone Scan	X						
EKG	X						
End Oral Therapy	X (e)						

- White blood cell count with differential, hemoglobin, hematocrit, platelet count, sodium, potassium, chloride, bicarbonate, blood urea nitrogen, creatinine, glucose, calcium, magnesium, phosphorus, ALT, AST, total bilirubin, alkaline phosphatase, lactate dehydrogenase, total protein, albumin
- Thoracic CT scan must be performed at a slice thickness of 5 mm or less
- For patients with serum creatinine >1.5
- These visits do not need to be performed at the study center, however, documentation of the required items must be sent to the study center as soon as they are available
- Saracatinib or placebo will be discontinued after 13 cycles (364 days) of therapy
- Prior to beginning oral therapy, treating physicians should obtain a full work-up to evaluate low or borderline low levels of phosphorus. (See section 3.3.3)
- Treatment evaluations/procedures should be performed within +/- 3 days.
- Treatment evaluations/procedures should be performed within +/- 3 days.

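### The three-year limit on survival contact for off-study patients has no start date and conflicts with the follow-up rules and power basis elsewhere in the protocol

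*Combined protocol and SAP*

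**What the plan says.** Four places in the combined protocol and SAP set the length of follow-up.

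- **Section 3.7.2 (Criteria for Removal from Protocol), after the toxicity criteria.** Patients taken off study are monitored for survival once a year through their physician, "for the duration that this study is open or a maximum of 3 years follow up". No start date is given for the three years.
- **Section 3.1.** "Patients will be followed for the duration that this study is open", with a projected total duration of six years.
- **Section 3.3.2.** In the text on withdrawal for toxicity, OS monitoring runs for the whole study, with no three-year limit.
- **Section 5.3.** Eighty-eight patients are accrued over 48 months, and the last is followed for a further year. For PFS, "this provides 80% power to detect a difference between the two resulting actuarial curves with a one-sided 0.10 alpha level log-rank test". For OS, "Evaluation of the 88 patients who are randomized, over the same time frame, will provide 85% power".

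The last visit and thoracic CT in the Section 3.4 chart are at month 36. The Appendix A table headed "Suggested Follow-up" ends at the same month. Section 5.3 does not truncate PFS or OS at 36 months.

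**The concern.** A site that follows Section 3.7.2 and a site that follows Section 3.1 or 3.3.2 could observe identical patients for different lengths of time. The limit is worded only for patients taken off study, but these are the patients who supply most deaths, because progression usually leads to removal.

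The power calculation lets a patient randomized at the start contribute up to 60 months. Under uniform accrual, (60 − 36)/48 = 50% of patients, 44 of 88, would have more than 36 months of potential follow-up at month 60. If their later deaths are not collected, OS rests on fewer events than Section 5.3 counts, in a trial that expects only about 36 deaths.

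**Working it through.** **Inputs from Section 5.3.** 44 patients per arm; one-sided alpha 0.10 (z = 1.2816); log-rank test; exponential survival; 48 months of accrual plus 12.

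- PFS at 2 years, 33% against 53%: hazards −ln(0.33)/24 = 0.0462 and −ln(0.53)/24 = 0.0265 per month; HR 1.746 (stated as 1.75).
- OS at 3 years, 45% against 70%: hazards −ln(0.45)/36 = 0.0222 and −ln(0.70)/36 = 0.0099; HR 2.239 (stated as 2.24).

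**Assumptions not in the documents.** Uniform accrual, no dropout, no effect of cross-over on OS, interim looks ignored.

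**Event probability for hazard λ, analysis at month 60.**

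- No cap: P = 1 − [exp(−12λ) − exp(−60λ)]/(48λ)
- Cap at 36 months from randomization: P = 1 − 0.5·exp(−36λ) − [exp(−12λ) − exp(−36λ)]/(48λ)

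Expected events are d = 44 × (P control + P saracatinib).

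- PFS, no cap: 44 × (0.769 + 0.588) = 59.7
- PFS, cap: 44 × (0.732 + 0.538) = 55.8 after rounding from unrounded probabilities
- OS, no cap: 44 × (0.528 + 0.293) = 36.2
- OS, cap: 44 × (0.478 + 0.255) = 32.2

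**Power, with Φ the normal distribution function.**

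- Schoenfeld: Φ(ln HR × √d / 2 − 1.2816)
- Freedman: Φ(√d × (HR − 1)/(HR + 1) − 1.2816)
- Exponential: Φ(ln HR / √(1/d1 + 1/d2) − 1.2816), where d1 and d2 are the events in each arm

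Example, OS by the exponential form. Without a cap, 0.806/√(1/23.25 + 1/12.91) = 2.322, so the power is Φ(1.040) = 85.1%. With the cap, 0.806/√(1/21.03 + 1/11.21) = 2.179, so the power is Φ(0.898) = 81.5%.

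| Endpoint and rule | Events | Schoenfeld | Freedman | Exponential | Log-rank simulation (20,000 trials) |
|---|---|---|---|---|---|
| PFS, month 60, no cap | 59.7 | 80.8% | 79.3% | 80.3% | 81.0% |
| PFS, month 60, 36-month cap | 55.8 | 78.9% | 77.3% | 78.1% | 79.3% |
| OS, month 60, no cap | 36.2 | 87.3% | 84.6% | 85.1% | 86.5% |
| OS, month 60, 36-month cap | 32.2 | 84.3% | 81.3% | 81.5% | 83.8% |
| PFS, month 72, 36-month cap | 61.2 | 81.6% | 80.1% | 81.0% | 81.5% |
| OS, month 72, 36-month cap | 36.2 | 87.3% | 84.6% | 84.9% | 86.7% |

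The uncapped rows reproduce the plan's 80% and 85%, most closely by the exponential form. The stated power therefore fits follow-up to month 60 without a three-year limit.

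**Three years counted from removal.** Taking progression as the time of removal, simulations under different assumed links between progression and death give OS power of 85.9% to 86.9% at month 60. The uncapped values are 86.5% to 87.3%. About 0.5 to 0.8 deaths are lost, and power falls by less than one point.

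**The case against.** A reader might infer that the stated 85% OS power is not delivered. The documents do not support that, for three reasons.

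- Section 3.7.2 applies the limit only to patients taken off study. The capped rows above apply it to all 88.
- The start of the three years is not defined. In a sentence about patients leaving the study, counting from removal is at least as natural, and simulated power then stays above 85%.
- Section 3.1 projects six years, and the extra year in Section 5.3 is a minimum. At month 72 the OS power under the strictest cap returns to about 85–87%.

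Even in the worst case at month 60, the shortfall against 85% depends on method. It is about one point by Schoenfeld (84.3%) or simulation (83.8%), and over three points only by the Freedman and exponential forms.

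A reader might also think that the 3-year OS estimate suffers. It does not: a Kaplan-Meier estimate at 36 months needs follow-up to 36 months, and later follow-up leaves it unchanged.

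Nor can a PFS loss be attributed to the Section 3.7.2 sentence, which concerns survival contact. Patients removed for progression already have their PFS event. The PFS loss arises only if PFS is censored where the scan chart ends, and no section says that it is.

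All of these objections stand, and they limit the size of the point. They do not reconcile the follow-up rules or supply the missing start date.

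**Conclusion.** The inconsistency is real and minor. One sentence caps survival contact for off-study patients at three years from an unstated date. Sections 3.1 and 3.3.2 set no such limit, and the Section 5.3 power is reproduced without one.

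In the worst case (36 months from randomization for everyone, analysis at month 60), the cap costs 4 of about 36 expected deaths and about 3 to 4 points of OS power by formula. Counted from removal, it costs about half a death and under one point. Separately, if PFS were censored at the month-36 end of the scan chart, PFS would lose about 4 events and 2 points of power.

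All of these figures rest on uniform accrual, no dropout and no cross-over effect. The point is to reconcile the rules for a small gain in precision; the sample size is not in error.

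**What to change.** 1. In Section 3.7.2, delete the clause that sets a three-year maximum. Use one rule throughout: annual survival contact for every randomized patient to the final data cut-off, in line with Sections 3.1, 3.3.2 and 5.3.
2. In Section 5.3, state that PFS is censored at the last adequate disease assessment when no scan follows month 36.
3. If the maximum is kept, define its start date and restate the OS power for that rule: about 81–84% at month 60 if it runs from randomization for all patients.

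The cost is a text amendment and a few more annual contacts through a procedure that already exists. No extra scans are needed.

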### **3.8 Post-Study Evaluation**

The following tests or procedures should be performed, if possible, at the time a patient is taken off of the study, regardless of the reason, unless the test or procedures have been performed within a period of four weeks.

- Physical examination
- ECOG performance status
- Assessment of clinical toxicity or adverse events
- Radiologic evaluation of progressive disease
- Laboratory studies
  - white blood cell count with differential
  - hemoglobin and hematocrit
  - platelet count
  - sodium, potassium, chloride, bicarbonate, blood urea nitrogen, creatinine, glucose
  - calcium, magnesium, phosphorous
  - ALT, AST, total bilirubin
  - alkaline phosphatase, lactate dehydrogenase, total protein, albumin

## **4 Supportive Care**

### **4.1 General**

The appropriate surgical care, antibiotics, blood product support and general supportive care measures will be administered by the treating physician, as clinically indicated.

### **4.2 Management of an Overdose with Saracatinib**

There is no known antidote for saracatinib and management of overdose should consist of symptomatic and supportive treatment. In view of the slow absorption rate of saracatinib, measures such as gastrointestinal lavage or administration of an emetic agent such as

activated charcoal or Ipecac syrup may be helpful if a patient is seen within two hours of taking an overdose.

Should an overdose occur, it must be recorded in accordance with the procedures described (see Section 7.2) regardless of whether the overdose was associated with any symptoms or not. All symptoms associated with the overdose should be recorded as adverse events. Oral therapy with saracatinib or placebo will re-commence at a time decided by the treating physician.

### **4.3 Procedures in Case of Pregnancy**

All patients must use adequate contraception during the study. However, should pregnancy occur, the patient will be removed from the study. Patients will be advised that the possible effects of saracatinib on the fetus are unknown.

Rodent reproductive toxicology studies have found that the administration of saracatinib resulted in effects on embryonic survival and fetal malformations at dose levels that were similar or lower than those likely to be achieved in humans. Some of the malformations included anophthalmia, microphthalmia, aglossia, micrognathia, cleft palate, kinked tail and hind paw hyperextension (33).

Should a pregnancy occur, it must be recorded in accordance with the procedures described (see Section 7.2). Pregnancy in itself is not regarded as an adverse event, unless there is a suspicion that an investigational product may have interfered with the effectiveness of a contraceptive medication.

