## 2 Eligibility Assessment and Enrollment

### 2.1 Eligibility Criteria

#### 2.1.1 Inclusion Criteria

Patients who have recurrence of osteosarcoma, localized to the lungs, who have had complete surgical removal of all lung nodules, are eligible for enrollment.

OR

Patients with suspected recurrence of osteosarcoma but have not had surgery are eligible for enrollment but will not be randomized until inclusion criteria (a) and exclusion criteria (b) are confirmed after surgery. If these are not confirmed, patient will be considered a screen failure and will not be randomized.

Other inclusion criteria are as follows:

- a. Histological diagnosis of osteosarcoma of the recurrent sample (histology types must be osteoblastic, chondroblastic, fibroblastic or telangiectatic). For patients enrolled prior to surgery, this criterion can be confirmed after consent, enrollment and surgical resection.
- b. Recurrence of osteosarcoma in the lung following standard chemotherapy including: adriamycin, cisplatin, ifosphamide and methotrexate (or provide justification why any of these agents were not received, for example, previous toxicity with methotrexate, or methotrexate not routinely given for adult patients)
- c. Age  $\geq 15$  and  $< 75$  years of age
- d. Weight  $\geq 34$  kg
- e. ECOG performance score of 0, 1 or 2 (0 = asymptomatic, 1 = symptomatic but fully ambulatory, 2 = symptomatic in bed  $< 50\%$  of the day)
- f. Adequate bone marrow function (ANC  $\geq 1500/uL$ , Hb  $\geq 9.0$  g/dL, platelets  $\geq 100,000/uL$ )
- g. Adequate renal function (serum creatinine  $\leq 1.5$  or a creatinine clearance  $\geq 50$  mL/min/1.73m^2)
- h. Adequate hepatic function (ALT/AST  $\leq 2.5X$  normal, total bilirubin  $\leq 2$  mg/dl with the exception of patients with Gilbert's syndrome)
- i. Adequate cardiac function (ECHO or MUGA with shortening fraction  $\geq 27\%$  or ejection fraction  $\geq 45\%$ ) and (EKG with QTc  $\leq 480$  msec)
- j. Negative pregnancy test for women of childbearing potential,  $\leq 7$  days prior to enrollment, and the willingness to use an acceptable method of contraception during participation in the study and for 3 months after the last dose

- k. Randomization must occur  $\leq 6$  weeks after complete surgical resection of all tumor nodules

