##### Medical

- Patients with radiographic or histologic evidence of disease progression who were receiving Saracatinib (see section 7.4.2)
- All patients with radiographic or histologic evidence of disease progression that is not confined to the lung(s)
- Patients with radiographic or histologic evidence of disease progression who were receiving placebo and are not amenable to surgical resection
- If the treating physician decides that it is in the best interest of the patient to be taken off the study
- Development of any concurrent medical condition that might preclude or contra-indicate the further administration of saracatinib/placebo
- Pregnancy
- Death

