#### 4.5 List of Contra-Indicated Medications

Saracatinib is substrate of CYP3A4 in humans. There are many drugs that either inhibit or induce CYP3A4 metabolism. This may result in increased or decreased exposure to saracatinib. The following tables list the drugs that are contra-indicated. In addition, the tables also list the minimum time period that the contra-indicated drug must be stopped, prior to the initiation of oral therapy with saracatinib or placebo.

Potent CYP3A4 inhibitors (may result in a 3-fold increase in exposure to saracatinib)

Contraindicated Drugs	Minimum period of discontinuation
Diltiazem	14 days
Clarithromycin (250 mg or 500 mg bid)	7 days
Erythromycin	7 days
Fluconazole 400 mg - lower doses (200 mg and 100 mg) are allowed	7 days
Itraconazole	7 days
Voriconazole	7 days
Ketoconazole	7 days
Indanavir	2 days
Nefazodone	2 days
Ritonavir	2 days
Saquinavir	2 days

Potent CYP3A4 inducers (may result in a 3-fold decrease in exposure to saracatinib)

Contraindicated Drugs	Minimum period of discontinuation
Barbiturates	14 days
Carbamazepine	14 days
Phenytoin	14 days
Rifabutin	14 days
Rifampicin	14 days
St John's Wort	14 days

Saracatinib is a moderate inhibitor of CYP3A4 in humans. There are many drugs that are CYP3A4 substrates. Therefore, patients who are receiving saracatinib may have increased exposure, pharmacological action or toxicity to CYP3A4 substrate medications due to inhibition of CYP3A4 by saracatinib. The following table lists the drugs that are contra-indicated. In addition, the table also lists the minimum time period that the contra-indicated drug must be stopped, prior to the initiation of oral therapy with saracatinib or placebo.

Contraindicated Drugs	Minimum period of discontinuation
Carbamazepine	14 days
Alfentanil	7 days
Cyclosporin	7 days
Tacrolimus	7 days
Atorvastatin	7 days
Lovastatin	7 days
Simvastatin	7 days

In addition, all of the medications listed above should not be restarted until 14 days after the last dose of oral therapy with saracatinib or placebo. They should never be restarted as long as the patient remains on oral drug therapy.

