### **6.5 Consent and Assent Processes and Documentation**

A signed informed consent document will be obtained prior to entry onto the study. The investigational nature and research objectives of this trial, the procedures and treatments

involved and their attendant risks and discomforts and potential benefits, and alternative therapies will be carefully explained to the patient and/or the patient's parents or guardians if she/he is a child. The investigators are requesting a waiver from the NCI IRB to allow only one parent or guardian to sign the informed consent to enter a child on the protocol. Because many patients must travel to the NIH from long distances at substantial expense, requiring both parents to be present for the consent process may adversely impact other children at home and pose financial hardship due to loss of work-related income. Other participating centers will have patients in similar circumstances and may request a similar waiver from their IRB.

The institutional Principal Investigator, or their designee, will meet with the patient, or the patient's parents or guardian, and other family members, to discuss the protocol treatment and alternative options. It will be stated clearly that participation in the research study is voluntary and that participants can withdraw from the study without losing benefits they would otherwise be entitled to. The patient and family members will be encouraged to ask questions, and additional meetings to discuss the treatment options will be arranged if necessary. The institutional Principal Investigator, or their designee, will then obtain consent from the patient. For patients who are <18 years of age, where deemed appropriate by the clinician and the child's parents or guardian, the child will also be included in all discussions about the trial and verbal or written assent will be obtained. The parent or guardian will sign the designated line on the informed consent form attesting to the fact that the child has given assent.

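### Section 4.3 scripts advice that fetal effects are unknown and omits the rodent malformation findings in its next paragraph; its contraception sentence should also repeat criterion j's period after the last dose

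*Combined protocol and SAP*

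**What the plan says.** Section 4.3 (Procedures in Case of Pregnancy) opens with the contraception rule: "All patients must use adequate contraception during the study". It then says that a patient who becomes pregnant is removed from the study, and gives the advice: "Patients will be advised that the possible effects of saracatinib on the fetus are unknown".

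The next paragraph of the same section summarises rodent reproductive toxicology. Saracatinib was associated with "effects on embryonic survival and fetal malformations at dose levels that were similar or lower than those likely to be achieved in humans", and seven malformations are named as examples.

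Two other places bear on the point:

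- **Section 2.1.1, criterion j** combines a negative pregnancy test for women of childbearing potential with "the willingness to use an acceptable method of contraception during participation in the study and for 3 months after the last dose".
- **Section 6.5** requires in general terms that "attendant risks and discomforts and potential benefits, and alternative therapies will be carefully explained to the patient".

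**The concern.** Section 4.3 does more than stay silent on the animal data: it prescribes what patients are to be told. A member of staff who follows that sentence can tell a patient that nothing is known, while the protocol holds adverse animal findings at dose levels relevant to humans. The sentence comes directly after the one about a pregnancy occurring, so it may be used when the patient most needs the fuller answer.

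Accurate advice and contraception also carry much of the protection on this trial. Section 2.2 and Appendix A schedule pregnancy testing at screening only, and the laboratory lists in Sections 3.4 and 3.8 contain no pregnancy test. Patients are eligible from age 15.

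The contraception wording is secondary. Read alone, 4.3 could be taken to mean that the obligation ends when a patient leaves the study. Early exit is foreseen: the removal criteria in Section 3.7.2 include "Patients with radiographic or histologic evidence of disease progression who were receiving Saracatinib".

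**Working it through.** No design figure (sample size, power, alpha or event count) is involved, so the check is a comparison of texts.

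**1. The advice against the data behind it**

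| Item in Section 4.3 | Content |
|---|---|
| Scripted advice | Effects on the fetus are unknown |
| Next paragraph | Embryonic survival affected and malformations seen in rodents, at dose levels similar to or below those likely in humans |
| Instruction to pass the rodent findings on | None |

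The two statements can both be true, because one may concern humans and the other concerns rodents. The advice is therefore incomplete rather than false.

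**2. Whether another section supplies the missing instruction**

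Section 6.5 requires risks to be explained but does not name reproductive findings. Neither the risk discussion in Section 6.3 nor the list of expected toxicities in Section 8.1.5 mentions them. The consent form is not in the available file, so it cannot be checked.

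**3. The contraception period**

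Let *t* be the time in months from the last dose until the patient leaves the study. Section 4.3 covers those *t* months. Criterion j covers 3 months after the last dose as well as participation. The difference in wording is max(0, 3 − *t*).

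- *Completes 13 × 28 = 364 days of treatment and stays in follow-up:* Section 3.4 lists visits to 36 months, so *t* is greater than 3 and the difference is 0.
- *Taken off study at the last dose, for example for progression on saracatinib:* *t* = 0 and the difference is 3 − 0 = 3 months.

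For the second patient, apart from the off-study evaluation and any toxicity monitoring, Section 3.7.2 provides this follow-up: "Patients who are taken off study will continue to be monitored for survival determination, annually by contacting the referring/treating physician". That contact is not a natural occasion to repeat contraception advice.

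The 0 to 3 months is a difference between two sentences. It is not a difference in what is required, because criterion j applies throughout.

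**4. Who is covered**

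Section 4.3 addresses all patients. Criterion j begins with women of childbearing potential and can be read as limited to them. Copying its 3 months into a sentence about all patients could therefore create a new requirement for men.

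**The case against.** The case against is a fair one:

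- The rodent findings sit one paragraph below the advice in a short section, so staff would have to use one sentence and ignore the next.
- What patients are told about risk belongs to consent, and Section 6.5 requires risks to be explained.
- On contraception, criterion j states the full period as a condition of entry, and 4.3 nowhere says that contraception may stop. Once a pregnancy has occurred, the contraception period is moot for that patient.

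The contraception argument largely stands, which leaves that part as an alignment edit. The first two arguments soften the advice point without removing it. The sentence prescribes content, and that content is weaker than the protocol's own data allow.

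A reader might infer more than the documents support:

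- **That patients were not told of the rodent findings.** The consent form is not available, so this cannot be said.
- **That the 40-hour half-life in Section 8.1.1 sizes the residual exposure.** Section 1.2.7 reports that half-life after single doses. It also says that accumulation on repeated dosing exceeded the single-dose prediction and that reduced clearance cannot be excluded. Section 1.2.5 reports bone-marker effects up to 24 days after dosing stopped. No remaining-drug figure is claimed.
- **That Section 4.5 shows 4.3 to be deficient.** Its rule that interacting drugs "should not be restarted until 14 days after the last dose of oral therapy" is only an analogy, since it concerns drug interactions.

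**Conclusion.** The point holds as a minor one. The advice sentence in 4.3 is incomplete on a serious safety matter, and the missing fact is already in the same section. The contraception sentence is compatible with criterion j but shorter on its face, by 0 to 3 months depending on when the patient leaves the study.

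This rests on reading the study as ending for a patient when that patient is taken off it. If annual survival contact counts as still being on study, the contraception ambiguity largely disappears, while the advice point is unaffected.

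The number of patients able to conceive is not given, so no count of those affected is offered. There is no effect on endpoints, power or analysis.

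**What to change.** Amend two sentences in Section 4.3.

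1. Replace the advice sentence with: *Patients will be told that effects on the human fetus are unknown, but that in rodents given saracatinib at dose levels similar to or below those expected in humans, embryonic survival was affected and fetal malformations occurred.*
2. Keep the contraception rule for all patients while on study and add: *women of childbearing potential must continue for 3 months after the last dose (Section 2.1.1, criterion j).*

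The sponsor should decide explicitly whether the post-dose period also applies to men, and word both sections to match.

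The cost is a short amendment and a check that the consent form agrees. Both changes use findings and a duration already in the protocol, and need no new data or visits.
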